9.4.10. Platelets and Hemoglobin

Platelet and hemoglobin measurements are not reliable with concurrent blood transfusions. Therefore, platelet values obtained from the day of a blood transfusion of platelets through 3 days after the transfusion will be excluded from all analyses. Hemoglobin values obtained from the day of a blood transfusion of either whole blood or packed red blood cells through 7 days after the transfusion will be excluded from all analyses. This rule will only be applied to postbaseline assessments of platelets and hemoglobin.

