4.2.3. Current SAP (version 4)

- In [Section 5.2.3](#), added text specifying that local laboratory results may be used for analysis when no central laboratory results are available. Text was also added to this section to address in vitro erythrocyte lysis referred to as table top hemolysis (TTH) caused by sample mishandling.
- In [Section 7.2.2.3](#) an example indicating patients to be included in a summary of response by visit was deleted as it was incorrectly implying that certain patients would be excluded from some time points.
- In [Section 9.4.10](#), added text indicating that the exclusion from analysis of hemoglobin and platelets results when concurrent with blood transfusion is only

applicable to postbaseline assessments. Because pre-treatment assessments, even if concurrent with blood transfusion, need to meet the inclusion criteria.

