5.1.2. Secondary Endpoints

The secondary efficacy endpoints of the study are the following:

1. Dialysis requirement status
2. Time to Complete TMA Response
3. Complete TMA Response status over time
4. Observed value and change from baseline in eGFR
5. CKD stage, as evaluated by eGFR at select target days and classified as improved, stable (no change), or worsened compared to baseline
6. Observed value and change from baseline in hematologic parameters (platelets, LDH, hemoglobin)
7. Increase in hemoglobin of ≥ 20 g/L from baseline, observed at 2 separate assessments obtained at least 4 weeks (28 days) apart, and any measurement in between
8. Change from baseline in QoL, as measured by EQ-5D-3L (all patients), FACIT Fatigue version 4 (patients ≥ 18 years of age), and Pediatric FACIT Fatigue (patients < 18 years of age) questionnaires

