7.2.2.7. Hemoglobin Response

The number and proportion of patients with an increase from baseline in hemoglobin $\geq 20\text{g/L}$, observed at 2 separate assessments obtained at least 4 weeks (28 days) apart, and any measurement in between will be summarized over time by presenting the number and proportion of responders along with a 2-sided 95% CI for each postbaseline time point.

A patient will be included in the analysis for a specific postbaseline time point if it was possible for the result at that time point to be confirmed (ie, the patient has to be in the study for a subsequent confirmatory assessment at least 28 days later). For example, a patient on-study at the Day 71 assessment and at the Day 99 assessment would be included in the Day 71 summary. However, a patient on-study at the Day 71 assessment that did not remain on-study until the Day 99 assessment or later would not be included in the Day 71 summary.

A set of summaries similar to the ones described above will be created without any requirement for a confirmatory result. This summary will be strictly based on a patient meeting the criterion at a specific time point.

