7.3.3. Other Safety

7.3.3.1. Analyses for Laboratory Tests

Observed values and changes from baseline in clinical chemistry, hematology, and urinalysis results will be summarized descriptively at baseline, and at each postbaseline time point. For laboratory results that can be classified as normal, low, or high based on normal range values, shifts from baseline in classification will be summarized for all study visits.

All data will be presented in listings, and a specific listing of abnormal results will be provided. For analysis purposes, laboratory results based upon standardized units will be used.

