9.4.9. Serum Creatinine and eGFR

Serum creatinine measurements are not reliable with concurrent dialysis. Therefore, all serum creatinine values obtained while a patient is on dialysis will be excluded from all analyses. Estimated Glomerular Filtration Rate (eGFR) will be imputed with a value of 10 (in mL/min/1.73 m²) while a patient is on dialysis. A patient will be considered on dialysis from the first day of dialysis through 5 days after the end of dialysis.

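### The transfusion rule can delete an uncontaminated same-day hemoglobin low, and it lets a patient transfused between two qualifying assessments count as a confirmed hemoglobin responder

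*SAP*

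**What the plan says.** SAP 9.4.10 reasons that counts taken around a transfusion cannot be trusted. For red cells and whole blood it removes "Hemoglobin values obtained from the day of a blood transfusion of either whole blood or packed red blood cells through 7 days after" the transfusion. For platelets, "platelet values obtained from the day of a blood transfusion of platelets through 3 days after the transfusion will be excluded from all analyses". Each window is tied to its own product. The rule is limited in time: "This rule will only be applied to postbaseline assessments of platelets and hemoglobin". It works by calendar day and says nothing about clock time.

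SAP 5.1.2 defines the hemoglobin endpoint as "Increase in hemoglobin of ≥ 20 g/L from baseline, observed at 2 separate assessments obtained at least 4 weeks (28 days) apart", and SAP 7.2.2.7 requires the rise to be "observed at 2 separate assessments obtained at least 4 weeks (28 days) apart, and any measurement in between". Entry to a visit's summary depends on the patient being on study long enough for confirmation. Transfusion is not mentioned there or in Protocol 15.8.2.7.

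No other section fills the gap. The carry-forward rule in SAP 7.2.1.1 covers components of Complete TMA Response, and hemoglobin is not one of them. The only sensitivity analysis (SAP 7.2.1.5) uses the Per Protocol Set. That set removes patients who had prohibited treatments, but Protocol 9.7 does not list red-cell or whole-blood transfusion among them.

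**The concern.** Two things follow from the wording.

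First, the exclusion reaches further than its own reason. A sample drawn before a transfusion on the same day is not affected by it, yet it is deleted with the later ones.

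Second, the response definition relies on intervening measurements to show that the rise was sustained. Once those values are deleted there is nothing left to fail the test, and the transfusion itself carries no weight. A patient who needed red cells between the two assessments is then reported in the same way as one who held the rise unaided.

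At stake is the meaning of one secondary endpoint, the confirmed hemoglobin response.

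**Working it through.** The plan states no figure that depends on this rule, so there is nothing to reproduce. The check applies the rule to the schedule.

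**Inputs.** Hematology visits after Day 1 from Protocol Table 1: Days 8, 15, 22, 29, 43, then every 14 days to 183 (15 visits). Windows from SAP 9.4.10: transfusion day t to t+7 for hemoglobin, t to t+3 for platelets. Response from SAP 7.2.2.7: at least +20 g/L at two assessments at least 28 days apart and at every retained value between. Assumptions: visits fall on their nominal days and there are no unscheduled samples.

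**1. Two transfusions.** Day 40 covers Days 40–47 and deletes visit 43. Day 54 covers Days 54–61 and deletes visit 57. With +20 g/L at Days 29 and 71, the gap is 71 − 29 = 42 days, no value is left in between, and the response is confirmed.

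**2. One low value.** Take +25 g/L at Days 71 and 99, −5 g/L at Day 85, and +10 g/L elsewhere. Days 71 and 99 are 28 days apart.

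| Transfusion | Day 85 value | Result |
|---|---|---|
| None | kept | no response |
| Day 77 | kept (window 77–84) | no response |
| Any of Days 78–85 | deleted | confirmed response |
| Day 86 | kept (window 86–93) | no response |

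The same low gives opposite results for transfusion on Day 85 and on Day 86. On Day 85 the sample may have been drawn first and be unaffected.

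**3. Extreme case.** Take a same-day transfusion at all nine visits from Day 43 to Day 155, and +25 g/L at the others. Days 8 and 169 qualify and nothing is retained between them that fails, so the response is confirmed.

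**4. Reach.** For transfusion days 2 to 183 (182 days):

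- Hemoglobin: 15 visits × 8 days = 120. Subtract 1 for Day 1, which lies outside the range, and 3 for days that hit two visits. That leaves 116 days that delete at least one scheduled value, and 182 − 116 = 66 that delete none.
- Platelets: 15 × 4 = 60 days delete one.
- Only 15 of the 182 days are scheduled visit days, where a same-day scheduled value can be lost.
- After Day 29 visits are 14 days apart, so one transfusion removes at most one scheduled hemoglobin value and the pair around it can survive.

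**5. Response rate.** With 50 evaluable patients (SAP 9.3), each reclassified patient is 1/50 = 2 percentage points.

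**6. By-visit means.** Retained mean − full mean = f × (retained mean − excluded mean), with f the share excluded. Both inputs are assumptions.

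| Excluded of 50 | Gap 20 g/L | Gap 40 g/L |
|---|---|---|
| 1 | +0.4 | +0.8 |
| 5 | +2.0 | +4.0 |
| 10 | +4.0 | +8.0 |

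If the excluded values average 10 g/L above the rest, 5 patients give 5/50 × (−10) = −1.0 g/L.

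**The case against.** The case for the rule is substantial. Most of the window (days 1 to 7) removes values that a transfusion may have raised, so compared with using them as measured the rule can be conservative. The windows are short, and a low drawn even one day before the transfusion stays and breaks the run. SAP 9.4.5 may also fill a visit with another value from its window. Baseline values taken near a transfusion are kept and averaged (SAP 9.4.2, 9.4.10), which can raise baseline and work against a 20 g/L rise. Hemoglobin is not part of the primary endpoint, and the study plans no formal tests (SAP 7.2.1.4). All of this stands. None of it gives a transfusion any role in the response definition or separates same-day samples by time.

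A reader might infer more, and the documents do not support it:

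- *By-visit means are biased upward.* This is plausible, since patients with low values are the ones likely to be transfused. But there is no transfusion rate and no hemoglobin gap in the documents, and the sign can change.
- *The means and the MMRM rest only on untransfused patients.* The rule deletes values, not patients. A transfused patient's other visits stay in the MMRM of SAP 7.2.2.6, which offsets the loss if the exclusions are missing at random.
- *Severe anemia vanishes from safety reporting.* Values can drop out of the by-visit summaries and of the tables where "shifts from baseline in classification will be summarized for all study visits". They remain in the listings (SAP 7.3, 7.3.3.1), and Protocol 11.4 requires clinically significant changes to be recorded as adverse events.
- *Dialysis shows the right treatment.* SAP 9.4.9 does say "Estimated Glomerular Filtration Rate (eGFR) will be imputed with a value of 10", but it also deletes serum creatinine on dialysis. Dialysis itself defines CKD Stage 5 in SAP 9.4.11, and the plan offers no such anchor for hemoglobin.

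**Conclusion.** The point holds for the hemoglobin response and for same-day samples. Followed exactly, the SAP can classify a patient transfused between two qualifying assessments as a confirmed responder, and it can delete an uncontaminated low drawn on the day of transfusion. Both follow from the wording and need no assumed rate.

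The size cannot be stated. It is 2 percentage points of response rate per affected patient out of 50, and the number affected depends on a transfusion rate that the documents do not give. It would also be too strong to say that such a rise was caused by the transfusion. In the Days 29 and 71 example the last window closes on Day 61, so under the SAP's own rule the Day 71 value is valid. What can be said is that the plan does not distinguish a rise that needed transfusion from one that did not.

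The consequence is limited to a secondary, descriptive endpoint, and the repair is cheap. How excluded platelet counts interact with carry-forward in the primary endpoint is not assessed here.

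**What to change.** 1. **SAP 7.2.2.7.** State that a whole-blood or red-cell transfusion between the first and the confirmatory assessment means hemoglobin response not met for that pair. Report the current deletion rule as a sensitivity analysis.
2. **SAP 9.4.10.** Keep every same-day value with a recorded time before the transfusion, whatever its level. Apply the exclusion only to later samples and to same-day samples of unknown time. Keeping only low same-day values would select data by outcome and should be avoided.

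Carrying pre-transfusion values forward as the main by-visit method is not recommended, and neither is returning post-transfusion values to the safety tables.

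**Cost.** The first change needs SAP wording and derivation code, using transfusion dates that the current rule already requires. The second needs clock times for the sample and the transfusion; where these were not recorded, the current exclusion simply continues. The hemoglobin response rate will be slightly lower and will also count transfusions given for reasons unrelated to aHUS, which the sensitivity analysis puts in view. If the timing rule is applied to platelets as well, it also reaches Complete TMA Response, because the platelet count is a component.

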9.4.2. Definition of Baseline Values

For the analysis, the baseline value is defined as the average of the values from the assessments performed prior to the first study drug infusion (these can include results from Screening and the Day 1 visit).

When a patient is on dialysis at baseline, then the first valid creatinine value to be used as the baseline value will be the first assessment ≥ 6 days post-dialysis. If a patient is on dialysis during the entire 26 week Initial Evaluation Period, then the baseline creatinine will not be calculated.

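### Transfusion-affected hemoglobin and platelet values are dropped after baseline but kept in it, so secondary gains are understated for patients transfused shortly before first dose, and no planned analysis shows by how much

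*SAP*

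**What the plan says.** SAP 9.4.10 starts from the position that "Platelet and hemoglobin measurements are not reliable with concurrent blood transfusions". It sets two windows. For platelets, "platelet values obtained from the day of a blood transfusion of platelets through 3 days after the transfusion will be excluded from all analyses". For hemoglobin, the rule covers values from the day of a "transfusion of either whole blood or packed red blood cells through 7 days after the transfusion will be excluded from all analyses". The section then limits its scope: "This rule will only be applied to postbaseline assessments of platelets and hemoglobin".

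SAP 9.4.2 defines baseline: "the baseline value is defined as the average of the values from the assessments performed prior to the first study drug infusion". It makes an exception for creatinine in patients on dialysis and none for transfusion.

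SAP 4.2.3 lists the scope limit as a version 4 change and gives the reason: "Because pre-treatment assessments, even if concurrent with blood transfusion, need to meet the inclusion criteria".

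This baseline feeds secondary endpoints 6 and 7 of SAP 5.1.2. SAP 7.2.2.6 summarizes change in platelets and hemoglobin and fits an MMRM. SAP 7.2.2.7 reports "The number and proportion of patients with an increase from baseline in hemoglobin" of at least 20 g/L, confirmed at least 28 days apart. The laboratory change and shift tables of SAP 7.3.3.1 also use a baseline.

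**The concern.** The same kind of sample is discarded after dosing and kept before it, so a transfused starting value may be compared with untransfused follow-up.

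The stated reason concerns eligibility, which is a separate use of the data. Criteria 2a and 2b may be met on local results from up to 28 days before Screening (Protocol 8.1, SAP 5.2.3), so the qualifying value need not be the baseline value. FAS membership turns on inclusion criterion 2c and exclusion criteria 1 and 2 (SAP 6.1), none of which uses hemoglobin or platelets.

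Elsewhere the SAP does not spare baseline. A creatinine baseline affected by dialysis is replaced by a later value (SAP 9.4.2), and samples hemolyzed by mishandling are dropped with no postbaseline limit (SAP 5.2.3).

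At stake is the accuracy of secondary estimates in a single-arm estimation study whose results are to be read beside prospective eculizumab studies (SAP 7.2.1). The named sensitivity analysis is the per-protocol repeat (SAP 7.2.1.5). The per-protocol criteria (SAP 6.2) do not mention transfusion, so that analysis would not reveal the problem.

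**Working it through.** The plan states no figure that depends on this rule, so there is none to reproduce.

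**Step 1. Which pre-dose samples the windows reach.** Screening runs from Day -7 to Day -1, with dosing on Day 1 (Protocol Table 1). Taking Day -1 as the day before Day 1, Day 1 is 7 days after Day -7 and 3 days after Day -3.

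- Red cells on Day -7: every hemoglobin value from Day -7 to Day 1 is inside the window.
- Red cells on Day -6 or later, before first dose: Day 1 is inside. Only samples from days before the transfusion are outside.
- Red cells on Day -14 to Day -8: some or all Screening values may be inside, but Day 1 is outside.
- Platelets on Day -3 or later, before first dose: the Day 1 platelet count is inside.

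**Step 2. True gain an affected patient needs.** From the SAP: threshold 20 g/L. Assumed, because the documents give neither: lift L = 10 to 20 g/L, and share of averaged pre-dose values affected s = 0.5 to 1.

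Required gain = 20 + L × s

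| L (g/L) | s = 0.5 | s = 1 |
|---|---|---|
| 10 | 20 + 5 = 25 | 20 + 10 = 30 |
| 20 | 20 + 10 = 30 | 20 + 20 = 40 |

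**Step 3. Understatement of mean hemoglobin change.** With f the share of patients affected (also not in the documents), understatement = f × L × s.

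- f = 5%: 0.05 × 10 × 0.5 = 0.25 g/L
- f = 10%: 0.10 × 10 × 0.5 = 0.5 g/L
- f = 30%: 0.30 × 10 × 0.5 = 1.5 g/L, or 0.30 × 10 × 1 = 3.0 g/L
- f = 40%: 0.40 × 20 × 1 = 8.0 g/L

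The MMRM uses baseline as a covariate, but its mean change at the average baseline still starts from the raised average, so adjustment does not remove the offset. The same formula applies to platelets in their own units. I put no number on it because the documents offer no lift.

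**Step 4. Illustration for the response rate.** Assume a normally distributed true gain with mean 30 and SD 20 g/L, judged at one assessment (the confirmation rule is ignored). Response probability = 1 - Φ((20 + L × s - 30)/20).

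- Clean baseline: 69.1%
- L = 10: 59.9% (s = 0.5) or 50.0% (s = 1)
- L = 20: 50.0% (s = 0.5) or 30.9% (s = 1)

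The group rate falls by f times the difference. At f = 10% that is 0.10 × (69.1 - 59.9) = 0.9 points up to 0.10 × (69.1 - 30.9) = 3.8 points. With means of 20 to 40 and SDs of 15 to 20 g/L, the fall at f = 10% lies between 0.7 and 5.0 points.

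**Step 5. Primary endpoint.** Its platelet criterion is an absolute count of at least 150,000 per microliter (SAP 5.1.1). Hemoglobin is not a component, and LDH and creatinine are outside the transfusion rule. No term of the endpoint uses the affected baselines.

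**The case against.** The strongest reply is that the choice was deliberate, does no harm to the main result, and is safer than the obvious alternative.

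- The primary endpoint is untouched. The error runs against the drug, so it cannot create a false signal of benefit. Observed values at each visit are also summarized (SAP 7.2.2.6), and postbaseline observed values do not depend on baseline.
- Averaging with an unaffected value dilutes any lift, and the whole magnitude is assumed.
- Removing transfused values from the main baseline could do worse. By Step 1, red cells given on Day -6 or later leave at most values from before the transfusion. If transfusions are given because hemoglobin is low (an assumption), those are selected low values. Regression to the mean would then inflate the gain in the drug's favor, with no control arm to show it. For a Day -7 transfusion no value from Day -7 to Day 1 remains.

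All of this stands, and it rules out replacing the main baseline. It does not answer the narrower point: eligibility does not require these values in the analysis baseline, a conservative error is still an error in an estimation study, and the plan neither counts the affected patients nor shows results without them.

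**Conclusion.** The asymmetry is real but limited. For patients with a pre-dose value inside the 7-day or 3-day window, gains in hemoglobin and platelets and the hemoglobin response may be understated. An affected patient would need a true gain of 25 to 40 g/L instead of 20. Mean hemoglobin change would be understated by f × L × s: 0.25 to 0.5 g/L at 5% to 10% affected with a 10 g/L lift on half the values, and 8 g/L at 40% affected with a 20 g/L lift on all values. Frequency, lift and share of values are all assumptions.

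The share s also depends on which baseline applies. Protocol 15.12.1 implies Day 1, with Screening as a stand-in. SAP 9.4.2 averages, and SAP 4.1 lists no change. On a single-value Day 1 baseline, s would be 0 or 1.

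A reader might infer more than the documents support:

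- That the primary response rate is biased. Step 5 shows it is not.
- That the rule flatters the drug. A raised baseline does the opposite.
- That the comparison is distorted for patients generally. It concerns only those transfused inside the windows, and the documents do not say how many there are or that such transfusion is common.
- That the limit is an oversight. SAP 4.2.3 shows a decision, though its reason covers eligibility only.

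**What to change.** Keep every pre-dose value for eligibility and keep the current baseline for the main summary. Then:

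1. Flag each patient with any pre-dose hemoglobin inside the 7-day window or platelet count inside the 3-day window, and report the number for each.
2. Add a sensitivity analysis of the hemoglobin response and of hemoglobin and platelet change that (a) excludes flagged patients, and (b) uses only pre-dose values outside the windows where any exist. In (b), patients with none keep their current baseline and are counted.
3. State beside (b) that it may rest on low pre-transfusion values and so may overstate gain. It should be read with (a) and the main summary, not in place of them.

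The cost is one flag and a few extra tables. No new collection should be needed: Protocol 9.6 records prior procedures from 28 days before Screening to first dose. The earliest transfusion that can matter falls 7 days before the first Screening sample, well inside that period, provided transfusions were entered with dates.

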9.4.11. Assignment of CKD Stage

Chronic kidney disease (CKD) stage will be classified based on the National Kidney Foundation Chronic Kidney Disease Stage as follows:

Table 6: Stages of Chronic Kidney Disease

Stage	Description	eGFR (mL/min/1.73 m ²)
1	Normal or High	≥90
2	Mildly Decreased	60-89
3a	Mildly to Moderately Decreased	45-59
3b	Moderately to Severely Decreased	30-45
4	Severely Decreased	15-29
5	Kidney failure	< 15 (or dialysis)

Note: In the absence of evidence of kidney damage, neither stage 1 nor 2 fulfill the criteria for CKD
 Source: [KDIGO 2012 Clinical Practice Guideline for the Evaluation and Management of Chronic Kidney Disease](#). 2013. 3: 19-62.

